
Section 6
 
Purpose and rationale Insert purpose, objectives and research questions/hypotheses here.
	
The purpose of this study is 1) to test the feasibility and acceptability of an online program to improve the self-efficacy when completing complex care tasks among family caregivers to individuals living with mid-stage Alzheimer's Disease (AD), and 2) to evaluate whether participation in this program is likely to affect mean levels of self-efficacy and mastery.
 
Research Questions:
 
 1) Can Learning Skills Together be feasibly delivered to family caregivers to individuals living with mid-stage Alzheimer's Disease (AD) online, and is online delivery of Learning Skills Together acceptable to caregivers? 2) Do caregivers to individuals living with mid-stage AD have increased self-efficacy and mastery following completion of the Learning Skills Together program? 
Primary hypothesis: Caregivers to individuals living with mid-stage AD will have higher self-efficacy and mastery scores, on average, after completing the Learning Skills Together program.
 
Study aims:
 
Aim 1: Develop a manual to train interventionists to deliver a standardized version of LST. An interdisciplinary team of healthcare faculty with experience delivering an earlier version of the classroom-based intervention will prepare the content of this manual and its accompanying caregiver workbook.
 
Aim 2: Conduct a pilot study to test study protocols and examine outcome data to inform a sample size calculation for an efficacy study. We will implement LST in using videoconferencing over 2 weeks. Pre-post surveys examining self-efficacy and mastery will be administered to participants (N=40) to: 1) examine for trends for these outcomes, and 2) obtain effect size estimates to inform the sample size for a future study to test intervention efficacy. Analyses will be conducted using paired t-tests.
 
Aim 3: Examine the feasibility of delivering LST, intervention fidelity, and caregiver satisfaction. We will collect data on fidelity through direct observation by the interprofessional team on the delivery of their profession specific content using a structured fieldnote guide and fidelity checklist. Barriers and facilitators to delivering and participating in the program will be evaluated in post-session telephone debriefings with interventionists, as well as one-on-one in-depth interviews with 10 participants. To evaluate caregiver satisfaction, we will collect survey feedback data from caregivers after the workshop and booster session.
 
Given the circumstances surrounding COVID-19, while updating the Learning Skills Together program, we propose to test the feasibility of delivering LST online to adhere to social distancing recommendations.

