Intervention. Learning Skills Together is a 4-session online intervention delivered using the Zoom videoconferencing platform. Caregivers will be emailed call information, including a password, prior to the scheduled sessions, and will be asked to login at the scheduled time. Prior to joining the videoconference sessions, caregivers participating in LST will first meet with an interventionist during a one-on-one scheduled telephone call to 1) make sure the caregiver is prepared to participate (e.g., caregiver is comfortable with technology used to deliver LST), 2) build trust with the interventionist, and 3) set up individual goals. The 4 group-based Zoom-delivered sessions lasting ~1.5 hours each will cover topics including managing behavioral symptoms of dementia, communication, oral hygiene and other common complex care issues caregivers frequently encounter when assisting someone with mid-stage AD. Presentations will integrate discussion and interactive activities delivered using multiple web-based tools (e.g., videos, downloadable PDFs, chat box, polls). Presentations will be based on materials developed by an inter-disciplinary team of healthcare professionals and compiled into a caregiver workbook that will include standardized materials (e.g., Powerpoint slide decks, handouts). Zoom “breakout” groups will be used to facilitate small group discussion and activities. Additional resource and post-session assignments will be sent to participants by email. One month after completing the 4-week program, caregivers will participate in a booster session in which they will reflect on their goals and raise further questions they may have encountered since program completion.

Data Collection. Data will be collected using an online, self-administered questionnaire using REDCap. Surveys will be linked with a unique identifier. Outcomes will be measured at baseline (up to 2 weeks prior to workshop) (T₀), 1 month later (T₁), and 1 month after the booster session (T₂).

Table 2: Summary of pre- and post-test survey measures

Construct	Measure
Targeted proximal outcomes	
Self-efficacy (overall)	Pearlin and colleagues (1991) Competence Scale ($alpha=0.74$) ³⁷

Self-efficacy (responding to disruptive behaviors)	Revised Scale for Caregiver Self-Efficacy (test-retest reliability= r=0.70) ⁹

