Self-efficacy conducting complex care tasks (investigator-generated through expert discussion)	How confident caregivers feel conducting each task and skill area taught during the LST intervention (0=Not confident at all; 5=Very confident) ³
Caregiver Mastery	Pearlin and Schooler (1978) Mastery Scale (alpha -0.78) ³⁸
Participant characteristics	e.g., age, gender, race, ethnicity, relationship to care recipient, years in role
Caregiving intensity	Functional ability of the care recipient ^{39, 40} , presence of behavioral symptoms of dementia ⁴¹ , subjective stress ^{42, 43}

Sample size and justification. We will recruit 40 caregivers to account for attrition, such that we will have a final sample of 34 caregivers. We estimated this sample size using a power analysis conducted in G*Power where we assume a large effect size ($d=0.50$) with a 2-tailed test at 0.80 power with an alpha of 0.05. The effect size, which may be arguably sizeable, is traditional for a pilot study; these data will inform subsequent power calculations in a future large-scale trial. ⁴⁴.

Aim 3: We propose multiple methods to examine the delivery feasibility, fidelity, and caregiver satisfaction.

Examining interventionists' fidelity to the training manual through direct observation. *Data Collection.* Each member of the interdisciplinary team responsible for developing the training manual will observe at least one workshop to examine how the section(s) they developed is(are) being implemented. Feedback will be recorded in a structured field-note worksheet as well as a checklist of essential components for delivery ⁴⁶. Checklists will be developed collaboratively while developing the training manual. A second observer will also observe each session to monitor fidelity. *Analysis:* Checklist scores from each observer will be summed at each session; we will calculate a kappa score to examine inter-rater reliability. Qualitative notes will be reviewed, and a content analysis will be applied to identify additional measures of fidelity and to refine existing items.

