Post-workshop telephone debriefings to examine barriers and facilitators to intervention delivery per interventionists. *Data collection:* After completion of each LST monthly program, we will conduct a telephone debriefing session with interventionists and students to discuss strengths and weaknesses in program delivery and ways to improve its administration. **One-on-one interviews to examine barriers and facilitators to delivery per caregivers, as well as application of training.** *Data collection:* In-depth semi-structured one-on-one half-hour interviews will be conducted with 10 participants. Caregivers will be asked about their experiences, including what they learned, barriers to participation, and changes they recommend, including how to improve LST's cultural relevance and tailoring to individual needs. *Recruitment.* We will circulate flyers at the workshop to recruit caregivers. Participant will be compensated \$20 for their time. **Reflective journals to evaluate caregiver learning and application of skills.** We will also collect caregivers' reflective journal entries to assess caregiver learning from all participants. Entries will be from worksheets completed for the booster session. *Analysis:* Discussion notes, transcribed interviews, and reflection worksheets will be analyzed with thematic content analysis, a method we selected for its flexibility ⁴⁷. Data will be iteratively coded by two members of the research team with input among the investigative team.

Self-administered surveys to assess caregiver satisfaction with LST. *Data.* All caregivers who participate in the LST intervention will receive a satisfaction survey immediately following the workshop and after the reflective booster sessions. Surveys will be completed online or by phone. Surveys will ask about satisfaction with each program component and the program's structure. *Analysis:* Descriptive statistics will be used to examine satisfaction survey data, including means, frequencies, and measures of dispersion.

9.2 Data Analysis Plan *Provide the plan for data analysis (include as applicable the sample size calculation).*

Aim 1:

Not applicable

Aim 2:

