We will compare scores on self-efficacy and mastery at T_0 , T_1 , and T_2 . We will first examine bar graphs for caregivers in aggregate and for each caregiver; the x-axis will be the assessment number (i.e., T_0 , T_1 , T_2) and the y-axis will be the targeted outcome scores. Next, we will compare the means and dispersion at each assessment point for each score. Finally, we will conduct t-test analyses to detect statistically significant differences in mean scores over time. *Exploratory analyses.* We will also complete exploratory analyses on stratified samples to assess differences in scores according to caregiver ethnicity and caregiving intensity. Although the sample size will likely be too small to observe differences, we may observe informative trends. Finally, we will compare the characteristics of participants who completed the intervention and those who dropped out to inform retention efforts in future studies.

Aim 3:

Discussion notes, transcribed interviews, and reflection worksheets will be analyzed with thematic content analysis, a method we selected for its flexibility⁴⁷. Data will be iteratively coded by two members of the research team with input among the investigative team.

4. Lorig K. Chronic disease self-management. *American Behavioral Scientist.* 2016;39:676-683

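### The only interview recruitment route stated is flyers at the workshop, so caregivers who never attend have no stated path to an interview and barriers to participation may be under-represented

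*Combined protocol and SAP*

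**What the plan says.** Section 6, Aim 3 sets the purpose: "Barriers and facilitators to delivering and participating in the program will be evaluated in post-session telephone debriefings with interventionists". The same sentence goes on to name one-on-one interviews with 10 participants as a further source.

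Section 9.1, Aim 3 gives the detail. On number: "In-depth semi-structured one-on-one half-hour interviews will be conducted with 10 participants". On content: "Caregivers will be asked about their experiences, including what they learned, barriers to participation, and changes they recommend". On recruitment: "We will circulate flyers at the workshop to recruit caregivers". Interviewees receive $20. The text describes no invitation by email, by phone or from the enrolment list, and no selection by attendance or completion.

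Four other statements bear on the point:

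- Format (Section 9.1, Intervention): "Learning Skills Together is a 4-session online intervention delivered using the Zoom videoconferencing platform". A booster session follows later.
- Contact before the first session (same place): "caregivers participating in LST will first meet with an interventionist during a one-on-one scheduled telephone call".
- Expected loss (Section 9.1, Sample size and justification): "We will recruit 40 caregivers to account for attrition, such that we will have a final sample of 34 caregivers".
- Use of information on dropouts (Section 9.2, Aim 2): "we will compare the characteristics of participants who completed the intervention and those who dropped out to inform retention efforts in future studies".

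**The concern.** The interviews ask what gets in the way of participating, but the stated route finds interviewees through participation. A caregiver who enrolled and never logged in is not at the workshop when flyers go round. One who left after a session or two has had fewer chances to see a flyer and probably less reason to respond.

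These caregivers have direct knowledge of what stopped them. Section 7 itself notes that attending several sessions is hard for caregivers because of care demands and geography. If their reasons are not collected, the evidence on research question 1 (feasibility and acceptability online) leans towards people for whom the programme was workable enough to attend. The future efficacy study would then inherit little information on why caregivers are lost.

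**Working it through.** **1. The plan's own figures.** Inputs from Section 6, Aim 2 and Section 9.1: paired t-test, d = 0.50, two-sided alpha 0.05, power 0.80. With n pairs, the noncentrality is d × √n on n − 1 degrees of freedom. At n = 34 this is 0.50 × √34 = 2.92, and exact power is 0.808; 34 is the smallest n that reaches 0.80. The stated final sample reproduces. The implied loss is 40 − 34 = 6, or 6/40 = 15%, and 34/(1 − 0.15) = 40.

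**2. What the 6 represents.** The 34 is the number needed for the paired comparison of survey scores, so the 6 are caregivers without analysable outcome data. A caregiver could attend every session and the booster and still not return the T2 survey one month later. Another could leave the programme and still return surveys. The documents give no expected number of never-attenders or programme dropouts.

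**3. Who can be reached.** Setting the route beside the groups of enrolled caregivers:

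| Group | Reached by flyers at the workshop? |
|---|---|
| Never attended a session | No stated path |
| Attended early, then left | Possibly; depends on when flyers circulate, which is not stated |
| Missed a session or skipped the booster | Often yes |
| Attended throughout | Yes |

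**4. Whether another source asks for reasons.**

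- Debriefings: these are held with interventionists and students, so any caregiver's reason arrives second-hand.
- Satisfaction survey: it goes to caregivers who took part and asks about programme components and structure.
- Reflective journals: these are the worksheets completed for the booster, so they come from those still engaged.
- Completer/dropout comparison: it covers characteristics, not reasons.
- Outcome surveys (Table 2): self-efficacy, mastery, participant characteristics and caregiving intensity.

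None asks a non-attender or dropout why.

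**5. Illustration under assumptions that are not in the documents.** Suppose 10 interviewees were drawn at random from 40 enrolled, D of them were programme dropouts, and everyone drawn agreed. The expected number of dropouts interviewed is 10 × D/40, and the chance of none is C(40 − D, 10)/C(40, 10).

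- D = 2: expected 0.5; chance of at least one 0.44.
- D = 6: expected 1.5; chance of none C(34, 10)/C(40, 10) = 0.155; chance of at least one 0.845.
- D = 12: expected 3.0; chance of at least one 0.98.

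For never-attenders the flyer route, taken literally, gives zero. For dropouts who attended at least once, no figure can be given.

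How far a barrier would be understated depends on how common it is in each group. Take 6 of 40 as dropouts, purely for illustration, and a barrier present in 20% of the other 34:

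- 20% in dropouts: overall 20%, so no understatement.
- 50% in dropouts: (34 × 0.20 + 6 × 0.50)/40 = 24.5%, against 20% if dropouts are not heard, a shortfall of 4.5 points.
- 80% in dropouts: (34 × 0.20 + 6 × 0.80)/40 = 29%, a shortfall of 9 points.

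The result runs from nothing to 9 points on assumed inputs alone.

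**The case against.** A reader might infer that everyone who drops out is shut out of the interviews. The documents do not support that. There are four sessions and a booster, the flyers are tied to the workshop and not to its last session, and interviewees need not be completers. Someone who came once and then withdrew could have received a flyer. Only never-attenders are clearly outside the stated route.

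A reader might also infer that flyers are the only route that will be used, or that they are seen only by people logged in. The plan is silent on other routes and does not rule them out. It does not explain how a flyer circulates on Zoom, and other materials are emailed to participants, so a flyer might be too. This calls for clarification, but no route for non-attenders is stated.

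Nor do the documents show that barriers will be understated: attenders are asked about barriers as well, and no figures by attendance are given. Treating 6 of 40 as the dropout rate would be a misreading.

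Two further objections have force. Aim 3 has several methods, and Section 6 assigns the debriefings to barriers to participating as well as delivering, so the interviews do not stand alone. The interviews also cover what was learned and how training was applied, on which never-attenders can say little. That is a good reason not to fix a quota for them. What survives is the gap itself: no planned source asks caregivers why they did not attend or why they left.

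**Conclusion.** The point holds in limited form. On the plan as written, enrolled caregivers who never attend have no stated path to an interview, and early leavers are less likely to be reached. Because Aim 3 and the interview topics include barriers to participation, and no other source collects reasons from these caregivers, such barriers may be under-represented. The direction is plausible, but the size cannot be computed from the documents.

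The conclusion rests on reading the flyer sentence as the whole recruitment plan for the interviews. If the investigators already intend to contact all enrolled caregivers, the text only needs to say so. The Aim 2 sample size and t-tests are unaffected. This is an inexpensive improvement to the qualitative part of a pilot whose purpose is to inform a larger study.

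**What to change.** Replace the flyer sentence in Section 9.1, Aim 3 with an invitation by email or phone to every enrolled caregiver, whatever their attendance, expressly including those who never logged in or withdrew. The study already has the means: registration is online or by phone, session details are emailed, and an introductory call is scheduled.

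Keep the 10 interviews and the $20 payment. Seek to include some non-attenders or dropouts among the 10; no fixed quota is needed. In the report, state how many interviewees were non-completers and whether any non-attenders or dropouts could be reached.

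The cost is a reworded sentence and a few extra messages or calls. Non-completers are harder to reach, and each interview with one says less about how the training was applied.

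### Aim 2's paired t-tests use only caregivers with both surveys, so score-related dropout can bias the effect size handed to the later trial, in a direction that cannot be known in advance

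*Combined protocol and SAP*

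**What the plan says.** Section 6, Aim 2 names the test: "Analyses will be conducted using paired t-tests". Section 9.2, Aim 2 applies it across the three surveys: "Finally, we will conduct t-test analyses to detect statistically significant differences in mean scores over time". That second sentence does not say paired; the word comes from Section 6.

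One stated purpose of Aim 2 is to "obtain effect size estimates to inform the sample size for a future study to test intervention efficacy". The sample size paragraph in Section 9.1 plans for loss: "We will recruit 40 caregivers to account for attrition, such that we will have a final sample of 34 caregivers". It assumes d=0.50 and a "2-tailed test at 0.80 power with an alpha of 0.05".

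The data collection paragraph in Section 9.1 sets three surveys, T0, T1 and T2, and links each caregiver's surveys by an identifier. Section 9.2 uses dropouts only once, in a comparison of their characteristics with those of completers, meant to help retention in later studies. No analysis set, missing-data method, repeated-measures model or sensitivity analysis is given for the effect estimate.

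**The concern.** A paired t-test discards a caregiver who lacks either of the two surveys being compared. If the chance of a missing T2 is related to scores, the mean change in those who remain need not equal the mean change in everyone enrolled.

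The protocol gives some reason to expect such a link. Section 7 says that care demands make multi-session in-person programs hard to attend, and that more severe behavioral symptoms go with lower caregiver self-efficacy, the outcome measured here. Online delivery may ease attendance, but it does not remove the care demands.

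The T0–T1 and T0–T2 contrasts could also rest on different caregivers. So could the means compared at each assessment, so part of an apparent trend may reflect who is left. What is at stake is the effect size passed forward. A confidence interval around it shows random error only and neither reveals nor covers selection.

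**Working it through.** **1. The plan's own figure.** For a paired t-test with d=0.50 and two-sided alpha 0.05, the noncentrality is d√n = 0.50 × √34 = 2.92 on 33 degrees of freedom. Power is 0.808 at n=34 and 0.795 at n=33, so 34 is the smallest n that reaches 0.80. Implied attrition is (40 − 34)/40 = 6/40 = 15%, and 34/0.85 = 40. The plan's 34 reproduces exactly and is a count of complete pairs.

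**2. What six missing caregivers can do.** Suppose the 34 completers show d=0.50 (SD of change 1) and the 6 dropouts have mean change m with the same SD. For all 40, mean = (34 × 0.50 + 6m)/40 and variance = 1 + 0.85 × 0.15 × (0.50 − m)².
- m = +0.25: mean 0.4625, variance 1.008, d = 0.46.
- m = 0: mean 0.425, variance 1.032, d = 0.42.
- m = −0.5: mean 0.35, variance 1.128, d = 0.33.

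**3. Assumed dropout mechanisms.** The documents give no mechanism and no correlation between visits, so these are scenarios. Three normal scores have unit variance and equal correlation r = 0.5 or 0.7 between all visits. The T1 and T2 means are raised by 0.5√(2(1 − r)), so the true T0–T2 d is 0.50. Logistic dropout after T1 is set to 15%, with odds 2 to 4 times higher per SD worse, and each scenario has 1,000,000 records. The all-data estimate regresses T2 on T0 and T1 in completers and predicts for everyone; this is the likelihood solution when people leave and do not return.

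| Dropout follows | Completers' d | All-data d |
|---|---|---|
| Nothing (random) | 0.50 | 0.50 |
| Small T0–T1 gain | 0.55–0.60 | 0.50 |
| Low T0 score | 0.42–0.46 | 0.50 |
| Both of these, equal weight per SD | 0.50–0.52 | 0.50 |
| Low T1 level alone | 0.50 | 0.50 |
| A stable unobserved level | 0.50 | 0.52–0.54 |
| The unseen T0–T2 change | 0.62–0.72 | 0.58–0.67 |

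Losing those with little gain leaves the better responders and raises d. Losing those with low T0 removes caregivers who would on average have risen most by regression to the mean, and lowers d.

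**4. Scale against sampling error.** Inverting the noncentral t for an observed d of 0.50 at n=34 gives a 95% CI of about 0.14 to 0.85. The biases from observed-score dropout are at most about 0.10 (0.60 − 0.50).

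**5. Precision.** With 20,000 simulated trials of 40 caregivers at r=0.5, and odds of dropout 2.7 times higher per SD less gain, the standard error is 0.168 for the all-data estimate and 0.169 for completers. Root mean squared error is 0.168 against 0.181, a fall of 0.013/0.181 = 7%.

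**The case against.** The case for leaving the plan alone has several parts that stand.
- Dropout related to observed scores does not always bias completers. Dropout that follows T1 level alone, under equal correlations, leaves d at 0.50.
- The two most natural mechanisms, little gain and low T0, pull in opposite directions and nearly cancel when they act together.
- Missing-at-random is not simply a weaker assumption than the one completers need; neither contains the other. If a stable unobserved level drives dropout, completers are right and the model is slightly off. If the unseen T2 change drives it, neither is right, though the model is closer.
- The gain is modest: about 7% in root mean squared error, in a scenario that favors the model.
- The documents do not say when the six are lost. Anyone lost before T1 contributes T0 only. Nor do they say whether caregivers who leave the program are still surveyed.

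A reader might infer that the effect size will be overstated, and that a later trial powered on, say, 0.57 instead of 0.50 would be about 23% too small, since (0.50/0.57)² = 0.77. The documents do not support this. They give no dropout mechanism, and an uncontrolled within-caregiver change is not a between-arm effect, so it does not translate directly into the size of a controlled trial.

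These points limit the size and certainty of the bias. They do not supply the missing-data plan that is absent.

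**Conclusion.** The concern holds as a possible bias. The stated test excludes an expected 15% of caregivers, nothing in the plan examines what that does to the effect size, and linked surveys already allow a better method. Under the stated scenarios, dropout related to observed scores moves completers' d from 0.50 to anywhere between about 0.42 and 0.60, and in several plausible cases hardly moves it. The direction is unknown and the shift is smaller than the sampling error at n=34. Unlike sampling error, it is systematic and would not show in the confidence interval. The figures rest on an assumed d of 0.50, loss after T1, equal correlations of 0.5 to 0.7, and dropout odds of 2 to 4 per SD; none but d=0.50 and the 15% comes from the plan. This does not invalidate the pilot. It is an inexpensive improvement that should be made.

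**What to change.** Make the main Aim 2 analysis one linear mixed model per outcome: visit (T0, T1, T2) as a categorical fixed effect, unstructured within-caregiver covariance, REML with Kenward-Roger degrees of freedom, and every enrolled caregiver with at least one score. Report the T1−T0 and T2−T0 changes with 95% confidence intervals.

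Keep the completers' paired t-tests as a sensitivity analysis. Add a second for dropout that depends on unobserved scores, for example a delta shift applied to the dropouts' missing values over a stated range. Report model and completer results together, since either can be the one that is off. State how many caregivers contribute at each visit, and whether those who leave the program are still asked to complete T1 and T2.

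The cost is analysis-plan wording and a little programming, with no new data, visits or participants. An unstructured covariance over three visits has six parameters, which 40 caregivers can support. The downside is reliance on missing-at-random, which the sensitivity analyses are there to probe.
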